6.2.6.2 Measurements of Treatment Compliance

DB Treatment Compliance

The by-subject listing of DB treatment compliance is provided for the safety analysis set, and displays results for DB treatment compliance parameters in separate columns: average DB exposure (tablets per month; see Section 6.2.6.1); percentage for DB tablet count compliance and odd study drug dosing day compliance; flags for the other parameters ("Y" or missing).

The frequency table of DB treatment compliance is provided by treatment group for the safety analysis set, and displays the following categories:

- DB study drug taken but not randomized
- DB tablet count compliance ≥ 80% from DB study drug start to later of last scheduled DBT Phase visit or DB study drug end/OL rimegepant start. Tablet count compliance is derived as 100 × cumulative DB exposure/required cumulative DB exposure, where
 - Cumulative DB exposure is defined in Section 6.2.6.1.
 - Required cumulative DB exposure is derived as follows:
 - Let n = DB maxdate DB study drug start date + 1.
 - DB maxdate is defined as the latest of the (1) Week 2, 4, 8, and 12 visit dates from the Visit Date DB CRFs, (2) Week 52/EOT visit date from the Visit Date OL CRF, if it is in the DBT safety analysis period (see Section 7.2), and (3) DB study drug end date.
 - If DB maxdate \geq OL rimegepant start date, then DB maxdate is set to OL rimegepant start date -1 day.
 - If n is even, then the required cumulative DB exposure is n/2.
 - If n is odd, then the required cumulative DB exposure is n/2 + 1.
- Average DB exposure (tablets per month) categories:
 - \circ > 16.8 (> 20% above EOD dosing)
 - \circ > 15.4 (> 10% above EOD dosing)
 - $\circ \geq 12.6 \text{ to} \leq 15.4 \ (\pm 10\% \text{ of EOD dosing})$
 - $\circ \geq 11.2 \text{ to} \leq 16.8 (\pm 20\% \text{ of EOD dosing})$
 - $\circ \geq 12.6 (\geq 90\%$ compliant with EOD dosing)
 - $\circ \geq 11.2 (\geq 80\%$ compliant with EOD dosing)
Average exposure is defined in Section 6.2.6.1.

- DB tablets taken per month for 3 consecutive months categories: $\geq 12, \geq 13$, and ≥ 14
 - Tablets per month are assessed by the number of 4-week (28-day) intervals in which a subject exceeded select tablet counts from the DB study drug start date to the DB study drug end date, where the number of 4-week intervals are consecutive (see Section 6.3.1.1 for months). For example, suppose a subject takes 20 tablets through 4 weeks, 10 tablets after 4 weeks to 8 weeks, and 25 tablets after 8 weeks to 12 weeks. Thus, this subject is not considered to have taken ≥ 14 tablets (more than EOD frequency) per month for 3 consecutive months.
- > 1 DB tablet taken on any 1 day
- ≥ 1 non-scheduled DB study drug dosing day (see Section 9.4)
- Incorrect DB study drug taken
 - All the time. Defined as as-treated treatment group not equal to as-randomized treatment group, i.e., any of the following:
 - Subjects randomized to rimegepant who took (1) ≥ 1 tablet from a DB placebo wallet, and (2) no tablets from a DB rimegepant wallet
 - Subjects randomized to placebo who took (1) ≥ 1 tablet from a DB rimegepant wallet, and (2) no tablets from a DB placebo wallet.
 - At least once. Defined as any of the following:
 - Subjects randomized to rimegpant who took ≥ 1 tablet from a DB placebo wallet
 - Subjects randomized to placebo who took ≥ 1 tablet from a DB rimegepant wallet.
- Time on study drug > 14 weeks.

Results for all categories are displayed, even those with 0 counts.

OL Rimegepant Treatment Compliance

The by-subject listing of OL rimegepant treatment compliance is provided for the safety analysis set, and displays results for OL rimegepant treatment compliance parameters in separate columns: average DB exposure (tablets per month; see Section 6.2.6.1); percentage for OL rimegepant tablet count compliance; flags for the other parameters ("Y" or missing).

The frequency table of OL rimegepant treatment compliance is provided by treatment group for the safety analysis set, and displays the following categories:

- OL rimegepant tablet count compliance ≥ 80% from OL rimegepant start to later of last scheduled OLE Phase visit or OL rimegepant end. Tablet count compliance is derived as 100 × cumulative OL rimegepant exposure/required cumulative OL rimegepant exposure, where
 - Cumulative OL rimegepant exposure is defined in Section 6.2.6.1.
 - Required cumulative OL rimegepant exposure is derived as follows:

- Let n = OL maxdate OL rimegepant start date + 1.
 - OL maxdate is defined as the latest of the (1) Week 14, 16, 20, 24, 28, 32, 36, 40, 44, and 48 visit dates from the Visit Date OL CRFs, (2) Week 52/EOT visit date from the Visit Date OL CRF, if it is in the OL rimegepant safety analysis period (see Section 7.2), and (3) OL rimegepant end date.
- If n is even, then the required exposure is n/2.
- If n is odd, then the required exposure is n/2 + 1.
- Average OL rimegepant exposure (tablets per month) categories: ≤ 14, > 14 to ≤ 16, > 16, ≤ 17, > 17, > 18, > 19, > 20, > 22, > 24, > 26. Categories with 0 counts overall are not displayed. Average OL rimegepant exposure is defined in Section 6.2.6.1.
- > 1 OL rimegepant tablet taken on any 1 day
- Time on OL rimegepant > 44 weeks
- OL rimegepant start on or before DB study drug end. Defined as nonmissing OL rimegepant start date on or before DB study drug end date.
- OL rimegepant taken but DB study drug never taken. Defined as nonmissing OL rimegepant start date and missing DB study drug start date.

Results for all categories are displayed, even those with 0 counts except where noted.

eDiary Usage Compliance

eDiary Usage Compliance during the OP and DBT Phase

The table of eDiary usage compliance during the OP and DBT Phase is provided by treatment group for the DBT safety analysis set.

eDiary DBT usage compliance is derived as follows:

• DB study drug start to later of last scheduled DBT Phase visit or DB study drug end/OL rimegepant start: 100 × (total number of efficacy data days from the DB study drug start date to the DB maxdate)/(total number of days from the DB study drug start date to the DB maxdate), where DB maxdate is defined previously.

eDiary DBT usage compliance is summarized as a continuous variable, and as the number and percentage of subjects in the following categories: $\geq 90\%$ compliance; $\geq 80\%$ compliance.

In addition, the number and percentage of subjects with ≥ 24 days of eDiary efficacy data in the first 28 days of the OP are also provided; see Section 7.2 for the 28-day OP analysis period and Section 9.2.2 for eDiary efficacy data days.

eDiary Usage Compliance during the OLE Phase

The table of eDiary usage compliance during the OLE Phase is provided by treatment group/OL rimegepant and overall for the OL rimegepant safety analysis set.

eDiary OLE usage compliance is derived as follows:

• OL rimegepant start to later of last scheduled OLE Phase visit or OL rimegepant end: 100 × (total number of efficacy data days from the OL rimegepant start date to the OL maxdate)/(total number of days from the OL rimegepant start date to the OL maxdate), where OL maxdate is defined previously.

eDiary OLE usage compliance is summarized as a continuous variable, and as the number and percentage of subjects in the following categories: \geq 90% compliance; \geq 80% compliance.

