2 STUDY DESCRIPTION

2.1 Study Design

This is a multicenter, randomized, double-blind, placebo-controlled study to assess the efficacy and safety of rimegepant in migraine prevention in Japanese subjects.

The study has 4 phases:

- Observation Phase (OP): Lasts approximately 28 days. Includes the Screening Visit and Prerandomization Evaluation Visit which must occur within 4 days of the Baseline Visit
- Double-blind Treatment (DBT) Phase:
 - Lasts up to 12 weeks, and includes the Baseline Visit, and Week 2, 4, 8, and 12/End of Treatment (EOT) Visits
 - Subjects are randomized 1:1 to one of the following 2 treatment groups at the Baseline Visit:
 - Rimegepant 75 mg dosed every other day (EOD)

- Placebo matching rimegepant 75 mg dosed EOD.
- Randomization is stratified by prophylactic migraine medication use (yes or no).
- Subjects are instructed that they can take a maximum of 1 orally disintegrating tablet (ODT) of double-blind (DB) study drug per every other calendar day.
- All randomized subjects who discontinue early from the DBT Phase should complete the EOT Visit. Otherwise, subjects should complete the Week 12 Visit.
- Open-label Extension (OLE) Phase:
 - Subjects who (1) complete the DBT Phase, (2) continue to meet all inclusion/exclusion criteria, and (3) have been compliant with the electronic diary (eDiary) may enter the OLE Phase, pending review of laboratory test results.
 - Lasts up to 40 weeks, and includes the Week 14, 16, 20, 24, 28, 32, 36, 40, 44, 48, 52/EOT Visits
 - Subjects are instructed that they can take a maximum of 1 open-label (OL) rimegepant 75 mg ODT (1) per every other calendar day on days they are scheduled to dose, and (2) as needed (pro re nata [PRN]) to treat a migraine on days they are not scheduled to dose.
 - All randomized subjects who discontinue early from the OLE Phase should complete the EOT Visit. Otherwise, subjects should complete the Week 52 Visit.
- Follow-up Phase:
 - Lasts up to 14 days and includes the Follow-up Week 2 Visit primarily for safety assessments. The Follow-up Week 2 Visit should occur approximately 2 weeks after the last visit in the last treatment phase (i.e., Week 12/EOT Visit if the subject did not enter the OLE Phase; Week 52/EOT Visit if the subject entered the OLE Phase).
 - All randomized subjects should complete the Follow-up Week 2 Visit, regardless of completing either treatment phase.

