 - DB tablet count compliance < 80% from DB study drug start to later of last scheduled DBT Phase visit or DB study drug end/OL rimegepant start
 - Incorrect DB study drug taken
- OL rimegepant dosing issue, defined as any of the following subcategories (see Section 6.2.6.2)
 - OL rimegepant tablet count compliance < 80% from OL rimegepant start to later of last scheduled OLE Phase visit or OL rimegepant end
 - \circ > 1 OL rimegepant tablet taken on any 1 day
 - OL rimegepant start on or before DB study drug end

- OL rimegepant taken but DB study drug never taken.
- eDiary usage compliance < 80% from DB study drug start to later of last scheduled DBT Phase visit or DB study drug end (see Section 6.2.6.2)
- eDiary usage compliance < 80% from OL rimegepant start to later of last scheduled OLE Phase visit or OL rimegepant end (see Section 6.2.6.2)
- Prohibited non-study medications, defined as any of the following subcategories:
 - o Atypical antipsychotics taken on or after informed consent #
 - Botulinum toxin type A taken on or after informed consent
 - Butterbur root or extract taken up to 14 days before randomization or afterward
 - Calcitonin gene-related peptide (CGRP) antagonist monoclonal antibody or small molecule taken on or after informed consent #
 - o Ergotamine taken on or after informed consent
 - o Lamotrigine taken on or after informed consent
 - o Lasmiditan taken up to 14 days before randomization or afterward
 - Narcotic (barbiturate or opioid) taken up to 2 days before randomization or afterward #
 - Select moderate or strong cytochrome P450 3A4 (CYP3A4) inducer taken on or after informed consent #
 - Select strong CYP3A4 inhibitor taken on or after informed consent #
 - Traditional Chinese medicine taken up to 14 days before randomization or afterward#. These are identified by the sponsor medical lead or designee from reviewing a list of unique therapeutic class and preferred names.
 - Triptan as non-study OL rimegepant concomitant medication (see Section 6.2.6.3) #.

For the subcategories marked with "#", preferred names are displayed alphabetically as additional subcategories. Medications taken up to X days before a reference date or afterward are defined as those with imputed medication start date or imputed end date \geq reference date -X. Refer to the Core SAP for additional details about prohibited non-study medications, except for CYP3A4 inducers and inhibitors which are defined below.

Medication Group	Preferred Name

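### The SAP's tablet-compliance rule for an odd number of days asks for half a tablet more than every-other-day dosing supplies, so borderline subjects could be wrongly placed below 80%

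*SAP*

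**What the plan says.** SAP section 6.2.6.2 defines double-blind (DB) tablet count compliance as "100 × cumulative DB exposure/required cumulative DB exposure". The day count is "Let n = DB maxdate DB study drug start date + 1"; a minus sign between the two dates has evidently been lost in the text conversion, so n is the inclusive number of days from first DB dose to DB maxdate. The denominator then has two branches: "If n is even, then the required cumulative DB exposure is n/2", and "If n is odd, then the required cumulative DB exposure is n/2 + 1". The open-label (OL) part of the same section repeats the odd branch: "If n is odd, then the required exposure is n/2 + 1". Neither place says that n/2 is truncated or rounded.

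The dosing being counted is set in SAP section 2.1: a "maximum of 1 orally disintegrating tablet (ODT) of double-blind (DB) study drug per every other calendar day".

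The result is used in three ways. The percentage is printed in a by-subject listing. A frequency table has the row "DB tablet count compliance ≥ 80% from DB study drug start to later of last scheduled DBT Phase visit" (section 6.2.6.2). The complement is a relevant protocol deviation in section 9.1: "DB tablet count compliance < 80% from DB study drug start to later of last scheduled DBT Phase visit". Section 9.1 has a matching OL deviation.

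**The concern.** When n is odd, n/2 ends in a half, so n/2 + 1 is never a whole number of tablets. The SAP would require 41.5 tablets over 81 days, for example. The form suggests that an integer-part operation was intended and left out.

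At stake is the accuracy of a reported compliance percentage and of a subject-level deviation flag. An inflated denominator lowers the percentage. It can therefore put a subject below 80% who belongs at or above it, but can never hide a true shortfall. It also invites disagreement between two programmers, one who codes the text as it stands and one who truncates n/2.

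**Working it through.** **Inputs.** The day count n, the two denominator rules, the compliance ratio and the 80% cut-off come from SAP section 6.2.6.2. The dosing interval comes from section 2.1. The double-blind phase lasts up to 12 weeks, which is 12 × 7 = 84 days.

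**Step 1: reproduce the part that is right.** Dosing on days 1, 3, 5, … up to day n gives n/2 doses when n is even: 14 over 28 days and 42 over 84 days. This agrees with the SAP's own exposure bands in the same section: 14 × 0.8, 0.9, 1.1 and 1.2 give 11.2, 12.6, 15.4 and 16.8 tablets per month.

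**Step 2: the odd rule.** The same count for odd n gives (n + 1)/2 doses. The SAP's figure exceeds it by (n/2 + 1) − (n + 1)/2 = 1/2 tablet at every odd n. A direct count of dosing days for n = 1 to 399 confirmed both branches. If n/2 is read as integer division, floor(n/2) + 1 equals (n + 1)/2 at every odd n, but the SAP does not state that reading.

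**Step 3: effect on the percentage.** A DB subject who takes exactly every scheduled dose scores 100 × [(n + 1)/2] / [n/2 + 1] = 100 × (n + 1)/(n + 2):

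- n = 1: 2/3 = 66.7%
- n = 3: 4/5 = 80.0%
- n = 15: 16/17 = 94.1%
- n = 83: 84/85 = 98.8%

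Full adherence falls below 80% only at n = 1.

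**Step 4: effect on the 80% cut-off.** The smallest passing tablet count is 0.4(n + 1), rounded up, by the correct rule and 0.4(n + 2), rounded up, as written. The line moves by 0.4 tablet, so the whole-tablet minimum changes only at some odd n. The odd values nearest 12 weeks, with the change at 71 shown for completeness, are:

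| n | Minimum, correct rule | Minimum, as written | Subject at the correct minimum |
|---|---|---|---|
| 71 | 29 | 30 | 29/36 = 80.6% becomes 29/36.5 = 79.5% |
| 79 | 32 | 33 | 32/40 = 80.0% becomes 32/40.5 = 79.0% |
| 81 | 33 | 34 | 33/41 = 80.5% becomes 33/41.5 = 79.5% |
| 83 | 34 | 34 | no change |
| 85 | 35 | 35 | no change |
| 87 | 36 | 36 | no change |
| 89 | 36 | 37 | 36/45 = 80.0% becomes 36/45.5 = 79.1% |
| 91 | 37 | 38 | 37/46 = 80.4% becomes 37/46.5 = 79.6% |

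The remaining odd values in this range (73, 75 and 77) also show no change. In all, 5 of the 11 odd values from 71 to 91 are affected, and 20 of the 50 odd values from 1 to 99. At each affected n, only one tablet count changes category.

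**The case against.** The best defence is that a requirement of 41.5 tablets is visibly impossible, so a programmer would truncate and get the right answer. The lost minus sign in the same list also shows that notation can disappear in conversion. This cannot be excluded. But the odd rule appears twice in the same form, and nothing in the text signals truncation. If the program does truncate, the written SAP does not describe it.

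The objections to the size of the effect largely stand:

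- **n = 1 is a corner case.** DB maxdate is the latest of the scheduled DB visits, a qualifying end-of-treatment visit and the last dose, so n = 1 needs one dose and no later counted visit.
- **The values next to day 84 are safe.** No 80% classification changes at n = 83, 85 or 87.
- **Open-label changes are probably rarer.** OL subjects may also take tablets as needed (SAP section 2.1), and cumulative OL exposure sums all tablets with a valid OL wallet number (section 6.2.6.1). Extra tablets can lift a subject past the raised line.

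A reader might infer that about half of all subjects are affected because half of all integers are odd. The documents give no distribution of n, and parity need not be random. Where DB maxdate is reset to the day before OL start, and OL starts on the next every-other-day slot, n is even and the rule is correct. Where DB maxdate is the last on-schedule dose, n is odd.

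**Conclusion.** The odd-n rule is wrong as written: half a tablet too high at every odd n, in both the DB and OL definitions, on the literal reading that n/2 is not truncated. The even-n rule is correct.

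The consequence is small. Near 12 weeks the percentage is about 1 point low. A wrong classification needs both one of the affected odd values of n and a tablet count exactly at the minimum. How many subjects meet both conditions cannot be known from the documents; it may be none.

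Two stronger readings are not supported. One is that protocol deviations will be over-counted; the documents support only that a borderline subject could be wrongly flagged. The other is that the efficacy results are affected. The analysis sets in SAP section 4.1 do not use tablet compliance, so the primary analysis and type I error are untouched. The effect is confined to descriptive compliance outputs and deviation tables and listings.

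The point concerns only the every-other-day prevention study that this SAP names as its own, C4951021 (section 1). It has no application to the supplied protocol, C4951022, in which one attack is treated on a single occasion (Protocol section 7.2.2).

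**What to change.** In both the DB and OL definitions in SAP section 6.2.6.2, state that when n is odd the required exposure is (n + 1)/2, or equivalently floor(n/2) + 1. Leave the even-n rule as it is. Then check that the compliance program matches, using a few odd values such as n = 1, 81 and 83, and confirm that the section 9.1 deviation flags draw on the same derivation.

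The cost is one short edit in two places and at most a small code change. No data collection, dosing instruction, analysis set or efficacy analysis changes.

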The design of the study is shown in Figure 1. Approximately 1064 subjects are screened to randomize up to approximately 490 subjects. It is estimated that approximately 400 subjects will enter the OLE Phase.

Figure 1 Study Schematic

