4 ANALYSIS SETS, TREATMENT GROUPS, AND SUBGROUPS

4.1 Analysis Sets

The following analysis sets are used for statistical analyses, as applicable:

- Enrolled: subjects who signed informed consent and were assigned a subject identification number by the interactive web response system (IWRS), i.e., nonmissing informed consent date. This analysis set is used mainly to assess study population and in by-subject listings.
- Full: subjects in the enrolled analysis set who were assigned a randomized treatment group by IWRS, i.e., nonmissing IWRS randomization date. This analysis set is used mainly to assess study population.
- Safety: subjects in the enrolled analysis set who take ≥ 1 dose of study drug (DB or OL), i.e., nonmissing study drug start date. This analysis set is used to assess study population, exposure, and on-treatment safety, and produce select by-subject listings.
 - \circ DBT safety: subjects in the safety analysis set who take \geq 1 dose of DB study drug

(rimegepant or placebo), i.e., nonmissing DB study drug start date. This analysis set is used to assess study population, exposure, and on-DBT safety.

- \circ OL rimegepant safety: subjects in the safety analysis set who take ≥ 1 dose of OL rimegepant, i.e., nonmissing OL rimegepant start date. This analysis set is used to assess study population, exposure, and on-OL rimegepant safety.
 - Interim safety: subjects in the OL rimegepant safety analysis set with OL rimegepant start date – DB study drug last date > 7 days. This analysis set is used to assess post-DBT pre-OL rimegepant safety.
- DB or OL rimegepant safety: subjects in the safety analysis set who take ≥ 1 dose of DB or OL rimegepant, i.e., nonmissing DB or OL rimegepant start date. This analysis set is used to assess study population, exposure, and on-DB or OL rimegepant safety.
- Follow-up safety: subjects in the safety analysis set whose last contact date is in the followup safety analysis period. This analysis set is used to assess follow-up safety.
- DBT efficacy: subjects in the full analysis set who (1) are randomized only once, and (2) take
 ≥ 1 dose of DB study drug. This analysis set is used mainly to assess outcomes research
 endpoints during the DBT Phase.

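### SAP 6.2.6.2 tabulates open-label compliance on everyone who took any study drug instead of those who took open-label rimegepant, and the matching listing names double-blind exposure

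*SAP*

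**What the plan says.** The OL part of SAP 6.2.6.2 plans two outputs.

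- The table: "The frequency table of OL rimegepant treatment compliance is provided by treatment group for the safety analysis set". Its first row is "OL rimegepant tablet count compliance ≥ 80% from OL rimegepant start to later of last scheduled OLE Phase visit or OL rimegepant end", calculated as "100 × cumulative OL rimegepant exposure/required cumulative OL rimegepant exposure". The other rows are bands of average OL exposure, more than one OL tablet on a day, time on OL above 44 weeks, OL start on or before DB end, and OL drug taken without any DB drug.
- The listing: "The by-subject listing of OL rimegepant treatment compliance is provided for the safety analysis set". Its columns include "average DB exposure (tablets per month; see Section 6.2.6.1); percentage for OL rimegepant tablet count compliance".

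SAP 4.1 defines the safety set by at least one dose of either DB or OL drug. It defines a narrower OL rimegepant safety set, for subjects with at least one OL dose, and gives exposure and on-OL safety among that set's uses. SAP 6.2.6.1 summarises OL exposure on the narrower set. Later in 6.2.6.2, the OLE eDiary compliance table is "provided by treatment group/OL rimegepant and overall for the OL rimegepant safety analysis set". For the Week 24 report, SAP 8.2 lists the 6.2.6.2 tables on the OL rimegepant safety set and the DB or OL rimegepant safety set only.

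**The concern.** A subject who took only DB drug has no OL start date. The compliance ratio does not exist for that subject, and none of the OL dosing events in the table can occur. Such subjects still belong to the set on which the table is to be produced. If they stay in the denominator, the printed compliance rate mixes two things: how well subjects took OL drug, and how many went on to the OLE Phase. Two arms with the same adherence could then show different rates only because different fractions continued.

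The listing has a separate fault that does not depend on any denominator. It shows DB exposure, while the table it accompanies bands OL exposure, so it cannot be used to check those bands.

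**Working it through.** **1. Does any row need the wider set?** Compliance, the average-exposure bands, more than one OL tablet on a day and time on OL are all built from OL dosing records. OL start on or before DB end requires a nonmissing OL start date. So does OL drug taken without DB drug, which is the one row that might seem to call for the wider set. Every subject who can meet a row is therefore already in the OL rimegepant safety set.

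**2. Which set do the neighbouring outputs use?**

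| Output | Set named |
|---|---|
| OL exposure (SAP 6.2.6.1) | OL rimegepant safety |
| OLE eDiary compliance (SAP 6.2.6.2) | OL rimegepant safety |
| 6.2.6.2 tables in the Week 24 report (SAP 8.2) | OL rimegepant safety; DB or OL rimegepant safety |
| OL tablet compliance (SAP 6.2.6.2) | Safety |

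The last line is the exception. Read literally, SAP 8.2 leaves this table out of the Week 24 report, which is the one focused on the OLE Phase. SAP Table 4 fits the same reading: the DB/OL column labels and a fixed overall column belong to the OL-based sets, not to the safety set.

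**3. Size of the dilution.** The SAP gives no expected compliance figure to reproduce. The inputs are:

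- About 490 randomized (SAP 2.1; 245 per arm in SAP 5).
- About 225 evaluable per arm, 450 in total (SAP 5). As a check on this count, 225 per arm with a 1-day difference, SD 3.75 and 2-sided alpha 0.05 gives power 0.807, matching the stated 80% or so.
- An estimate that "approximately 400 subjects will enter the OLE Phase" (SAP 2.1), taken here as the number with at least one OL dose.
- The number treated is not stated. I take N = 450 to 490 as an assumed range.

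Share with no OL drug = (N − 400)/N. Ceiling of the row = 400/N. Printed rate = true rate × 400/N.

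| N treated | No OL drug | Ceiling | True 80% prints as | True 90% prints as | True 95% prints as |
|---|---|---|---|---|---|
| 490 | 90/490 = 18.4% | 81.6% | 65.3% | 73.5% | 77.6% |
| 470 | 70/470 = 14.9% | 85.1% | 68.1% | 76.6% | 80.9% |
| 450 | 50/450 = 11.1% | 88.9% | 71.1% | 80.0% | 84.4% |

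The true rates of 80%, 90% and 95% are illustrations. The result also moves with the OLE estimate. For N from 450 to 490, the share with no OL drug is 20.0% to 26.5% if 360 enter and 6.7% to 14.3% if 420 enter. On the OL rimegepant safety set the share is zero and the row can reach 100%.

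**4. Listing.** The exposure column in the OL listing is the same as in the DB listing earlier in the section, while the OL table bands average OL exposure. Carry-over from the DB text is the likely explanation.

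**The case against.** A reader might infer that about 18% of treated subjects would be counted as non-compliant. The documents do not support this. The compliance table has no row for below 80%. A below-80% category for OL tablet count appears among the relevant protocol deviations in SAP 9.1, but it too is measured from OL start, which these subjects lack. At most they dilute a percentage. The 18% is also 90 of 490 randomized, and so is the upper end of the range for treated subjects.

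The dilution itself is conditional. SAP 6.1.2 leaves counting rules for frequency tables to the Core SAP, and SAP 6.1.1 leaves table templates to a separate mock document. If those restrict the denominator to subjects with OL data, the percentages would be right. Nor can one say that every exposure band is wrong. If average OL exposure is missing for DB-only subjects, the counts are unaffected and only the percentages shift. If it were set to zero, these subjects would fall into the lowest bands and inflate them. The SAP does not say which applies.

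Other outputs limit the damage. OL exposure is summarised on the right set, and the study drug listing in SAP 6.2.6.1 gives doses and time on OL, so average OL exposure can be derived for each subject. No comparison of OL compliance between arms is planned.

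These points stand, and they reduce the severity. They do not remove the mismatch in the named set, nor the wrong variable in the listing, which is an error whatever the counting rules say.

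**Conclusion.** Wrong as written, and minor. The set named for the OL compliance table does not fit its rows and conflicts with SAP 6.2.6.1, with the eDiary paragraph of 6.2.6.2 and with SAP 8.2. The listing names the wrong exposure variable. If percentages use the named set, about 400 subjects take OL drug and 450 to 490 are treated, then 11% to 18% of the denominator has no OL drug, the row for at least 80% compliance is capped at 81.6% to 88.9%, and a true 90% prints as 73.5% to 80.0%. The Core SAP could remove the dilution but not the inconsistency.

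Only descriptive output is affected, in the primary-completion and last-visit reports (SAP 8.1 and 8.3). No efficacy test, alpha level or power changes. The finding rests on the SAP alone. That SAP is written for C4951021, the prevention study, while the protocol supplied is for C4951022, an acute-treatment study with no extension phase.

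**What to change.** In SAP 6.2.6.2:

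- Produce the OL compliance table on the OL rimegepant safety analysis set, with the presentation already used for OLE eDiary compliance: "provided by treatment group/OL rimegepant and overall for the OL rimegepant safety analysis set". Under SAP Table 4 this gives the columns DB Rimegepant/OL Rimegepant, DB Placebo/OL Rimegepant and Overall.
- In the OL listing, replace average DB exposure with average OL rimegepant exposure as defined in SAP 6.2.6.1. The listing may stay on the safety set, since it has no denominator.

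The cost is two wording changes and the matching table and listing templates. No row is lost, no data collection changes, and the table then falls within the Week 24 report as SAP 8.2 describes it.
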